9 STATISTICAL REPORT SECTIONS

9.1 Summary of analysis.

This analysis will show the following tables and figures:

Figure 1. Patients enrolled and included in the study.

Table 1. Description of the analysis population. Descriptive statistics. All patients enrolled.

Table 2. Patient baseline characteristics. Descriptive statistics. Full analysis and per-protocol set.

Table 3. Patients who achieve a significant inhibition in the histological score between the post-treatment and pre-treatment period. Inferential statistics. Full analysis and per-protocol set.

Figure 2. Difference between the baseline and post-treatment levels of biomarkers (cyclin D1, Ki67, active caspase 3 and PARP1). Inferential statistics. Full analysis and per-protocol set.

Figure 3. Correlation between the levels of biomarkers with significant inhibition and PARP1. Inferential statistics. Full analysis and per-protocol set.

Figure 4. Change between baseline biomarker levels (PARP1 and with significant inhibition) depending on the mutation or deficiency identified (including MSI). Inferential statistics. Full analysis and per-protocol set.

Table 4. Adverse events observed in the study, occurred at least in 10% of patients. Descriptive statistics. Safety analysis.

Table 5.- Plasma concentrations of the drug for each patient by time.

Figure 5.- Mean plasma level curve of the drug by time.

9.2 Study full analysis.

9.2.1 Patients recruited, enrolled and disposition of patients in the study.

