4 OBJECTIVES AND ENDPOINTS

4.1 Study objectives

Primary Objective: The primary objective of this study is to identify anti-tumor biological efficacy by measuring, in human tumor samples, biomarker changes associated with short exposure to AZD2281 as potential predictors of activity in endometrial carcinoma (EC). This is an exploratory study with a biological primary endpoint.

Secondary objectives:

- To estimate the tolerability to AZD2281 throughout the study and up to 28 days after the last dose of AZD2281.
- To correlate changes induced by AZD2281 with the different type of endometrial carcinoma and other tumor biomarkers (NFkBp65 and p50, PARP, PARP-1, pHistone 2AX, pHistoneH3, VEGF (Vascular Endothelial Growth Factor), HIF(Hypoxia inducible factor)-1alpha).
- To estimate the predictive potential with regard to the following biomarkers (immunostaining for PTEN (phosphatase and tensin homolog), MLH-1 (mutL homolog 1), MSH-2 (mutS homolog 2), MSH-6 (mutS homolog 6), PMS-2 (Postmeiotic Segregation Increased S. Cerevisiae. 2).

- To estimate the potential predictive role of microsatellite instability (MSI) and PTEN loss in clinical tumor changes and PARP inhibition.
- To correlate clinical tumor changes with several targets of PARP inhibition.
- To further explore the use of Pharmacokinetic-dynamic modeling (PBMC modeling) as surrogate pharmacodynamic marker of AZD2281 activity in endometrial tumors.
- To establish a pharmacokinetic-dynamic modeling, based on the status of the variables of time (t), concentration (C) in blood, and molecular effect (E). PK-PD analysis will be performed based on the plasma concentration - PARP inhibition % in the tissue.

Secondary initial objectives that were dismissed:

- To quantify AZD2281 levels in human tissues after the oral administration of the drug.
- To explore the correlation between intratumoral AZD2281 concentrations with plasma PK parameters and molecular alterations in EC after AZD2281 treatment.
- To compare intratumoral AZD2281 concentrations with those present in healthy tissues.
- To establish a pharmacokinetic-pharmacodynamic modeling, based on the status of the variables of time (t) and concentration (C) in the tissue.

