5 STUDY DESIGN

5.1 Study design

(ICH E3;9.)

This is an open-label, non-randomized, uncontrolled, multicenter phase 0 study that will enroll approximately 36 patients. No efficacy objectives are included in this study. Randomization, blinding or control group are not required in this study design. The schedule of the assessments and the procedures performed in the patient is described in Tables 1 and 2.

Table 1. Study Schedule

[figure not shown]

Table 2. Study Procedure Schedule

Study procedures	SCREENING From Day (-14) to Day 0	START From Day (-7) to Day 0	TREATMENT PERIOD From Day 1 to Day 28 (+/- 5 days)	SURGERY or CT-biopsy Day 29	FOLLOW UP 28 days after the last dose of the drug
Signed informed consent		X			
Anamnesis and physical examination		X			
Concomitant medication record		X	D7-D14-D21-D28		
Performance status (WHO) and vital signs		X	D7-D14-D21-D28		X
Safety assessment (CTCAE v 4.1)		X	D7-D14-D21-D28		X
Imaging evaluations		X			
Standard laboratory procedures					
Pregnancy test		X			
Hematology/biochemistry values		X	D7-D14-D21-D28	X	X
Experimental laboratory (sample collection)					
Blood sample	BS1 BS2 BS3 BS4 BS5 BS6 BS7		D1 (Before the first dose) D1 (After the first dose) D7 D14 D21 D28		
Formalin-fixed, paraffin embedded (FFPE) tumor tissue	X			X	
Frozen tumor tissue	X ₍₁₎			X	
Tumor tissue samples will be obtained as follows:					

- Biopsy: At least one paraffin embedded biopsy will be obtained prior to initiating the therapy period.
 - (1) It will be recommended to collect the frozen tissue samples, if possible.
 - Surgical tumor sections or biopsy samples will be obtained in the 24 hours following the last dose of study treatment. In case that surgical tumor sections are taken, 50% will be frozen and 50% formalin-fixed and paraffin-embedded. In the case that biopsy samples are taken, at least 2 tumor samples will be obtained, 50% will be frozen and 50% paraffin embedded.

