7 STATISTICAL METHODS

7.1 General considerations

The demographic and baseline numeric variables will be summarized by the number of patients, the number of valid patients, mean, standard deviation, median, quartiles, maximum and minimum. The frequency and percentages based on the total of patients in the analysis set will be reported for the categorical variables. Quantitative variables will be summarized by the number of patients, mean, median, 95% confidence interval, standard deviation, quartiles, minimum and maximum, as appropriate. Qualitative variables will be summarized by the frequency, the percentage and the confidence interval of the odds ratio, where appropriate.

Time-to-event variables will be summarized by showing the number of events, percentage, median survival with its 95% confidence interval, and will be analyzed through the Kaplan-Meyer method.

The evolution of quantitative variables will be analyzed through the Wilcoxon's non-parametric test, mean difference, medians and their 95% confidence intervals.

The evolution of qualitative variables will be analyzed through the McNemar test.

No inferential statistics will be performed for baseline variables or safety variables, unless otherwise specified.

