The study treatment was not administered according to the protocol: < 23 days or > 33 days	Treatment	No	Case by case	Case by case	Case by case	Case by case
The study treatment was not administered according to the protocol: dose > 600 mg/day	Treatment	No	Case by case	Case by case	Case by case	Case by case
The study treatment was not administered according to the protocol: Patients did not comply with the administration up to 3 days prior according to the protocol (>3 days for any reason).	Treatment	No	Case by case	Case by case	Case by case	Case by case
The study treatment was not administered according to the protocol: Patients did not comply with the minimum 50% (14 days) drug administration.	Treatment	No	Case by case	Case by case	Case by case	Case by case
The study treatment was not administered according to the protocol: Patients did not comply with the administration margin >6 days (3+3) for any reason.	Treatment	No	Case by case	Case by case	Case by case	Case by case
Toxicities not managed according to the protocol	Treatment Safety	No	Case by case	Case by case	Case by case	Case by case

(dose interruption/reduction, study treatment discontinuation/withdrawal not performed according to the protocol, toxicities not followed up 28 days post-treatment).						
The pre-treatment biopsy (MT1) was not collected.	Treatment	No	No	Case by case	No	
The pre-treatment biopsy (MT1) was not performed according to the protocol (biopsy date > 14 days prior to treatment start).	Biomarker analysis	No	Case by case	Case by case	Case by case	
The post-treatment surgery/biopsy was not performed according to the protocol (it was not performed +4 days upon end of treatment or any of the samples [MT2 paraffin/frozen, MNT2 frozen] was not collected).	Biomarker analysis	No	Case by case	Case by case	Case by case	
Pre-treatment blood sample was not collected according to the protocol (MS1 not collected or not collected before the first dose).	Biomarker analysis	No	Case by case	Case by case	Case by case	
Post-treatment blood sample in post-treatment was not collected according to the protocol (some of MS2 to MS7 samples were not collected, MS2 to MS6 samples were not collected 1-4 hours after	Biomarker analysis	No	Case by case	Case by case	Case by case	

the dose and/or MS7 sample was not collected 24 hours before the surgery).						
The patient was withdrawn from the study.	Safety	No	Case by case	Case by case	Case by case	Case by case

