Serious concomitant diseases, including diseases that may interfere with drug absorption.	Safety	No	Case by case	Case by case	Case by case	Case by case
Visits performed outside of the window (Screening > 14 days, visits D7 to D28 > 7 ± 3 working days or follow-up visit > 35 days after the last dose).	Procedures	No	Case by case	Case by case	Case by case	Case by case
Screening assessments performed > 28 days prior to treatment start.	Procedures	No	Case by case	Case by case	Case by case	Case by case
D1 test performed > 3 days prior to treatment start date or not performed.	Procedures Safety	No	No	No	No	No
D7 to D28 tests, surgery and follow-up not performed one day prior or on the same day as the date of the visit or not performed.	Procedures Safety	No	No	No	No	No
Any test value not performed.	Procedures	No	No	No	Case by case (PK-PD Modeling)	Case by case (PK-PD Modeling)

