9.2.4 Safety analysis

9.2.4.1 *Treatment exposure analysis*

(Treatment delays, reductions and discontinuations, duration in days and strength of the dose received).

9.2.4.2 *Analysis of adverse effects*

(All serious related adverse effects, discontinuations, deaths and other relevant events).

9.2.4.3 *Analysis of concomitant medication received*

9.2.4.4 *Analysis of the physical examination and other safety-related remarks*

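### As titled, SAP Table 4 lists adverse events over the whole study with no stated split at surgery, so common on-drug and post-operative events can share a row

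*SAP*

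**What the plan says.** SAP 4.1 sets the secondary objective "To estimate the tolerability to AZD2281 throughout the study and up to 28 days after the last dose of AZD2281". The only adverse event table in the SAP 9.1 list is Table 4, described as "Adverse events observed in the study, occurred at least in 10% of patients" and marked as descriptive. It is visible by title only.

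On timing, the notes to Table 2 in SAP 5.1 state: "Surgical tumor sections or biopsy samples will be obtained in the 24 hours following the last dose of study treatment". The deviation list in SAP 8 flags the procedure if "it was not performed +4 days upon end of treatment", and the same row also covers samples that were not collected. The schedules in protocol Appendix 1 and SAP 5.1 place the CTCAE safety assessment at baseline, on D7, D14, D21 and D28, and at follow-up 28 days after the last dose. The Day 29 column is headed as surgery or biopsy, so not every patient need be operated on at that point.

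SAP 5.1 describes the study as uncontrolled. SAP 7.2 makes the full analysis set, all treated patients, the safety set. Outside Table 4, SAP 9.2.4.2 plans to report "All serious related adverse effects, discontinuations, deaths and other relevant events". SAP 7.3 names days since surgery, but only as a factor in the biomarker subset analysis.

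**The concern.** The objective concerns the drug, but the window over which events are collected includes an operation. An event such as nausea, pain or anaemia may arise on treatment or in the weeks after surgery. If Table 4 counts each patient once per event over the whole study, its reader cannot tell which of the two a row reflects. There is no comparator to show what surgery alone contributes.

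What is at stake is how well the table describes common non-serious events. The trial gives the drug up to the day before surgery, so it can describe tolerability before the operation separately. A single whole-study count gives that up.

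**Working it through.** The plan states no figure to reproduce here. The check compares the safety window with the date of surgery, then asks what a row of Table 4 can show.

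**Inputs**
- N = 36 (SAP 5.1 and 5.4), taking all 36 as treated.
- Drug days D = 28, allowed range 23 to 33 (28 ± 5; protocol synopsis, Therapy).
- Safety follow-up F = 28 days after the last dose (SAP 4.1).
- Lag L from last dose to surgery: 1 day as scheduled (Day 29). The range is 0 days (procedure within 24 hours) to 4 days (SAP 8).

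**Cut-off for a row.** 0.10 × 36 = 3.6, so at least 4 patients; 4/36 = 11.1%.

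**Calendar share after surgery, operated patients.** Share = (F − L)/(D + F).
- As scheduled: (28 − 1)/(28 + 28) = 27/56 = 48%.
- Lowest: D = 33, L = 4, giving 24/61 = 39%.
- Highest: D = 23, L = 0, giving 28/51 = 55%.

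**Share by scheduled assessment.** The post-baseline CTCAE assessments are D7, D14, D21, D28 and follow-up. Four are on drug and one is after surgery, so the share is 1/5 = 20%.

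**What a row can show.** With one whole-study count, a row at the minimum of 4 of 36 is compatible with anything from 0 of 36 to 4 of 36 patients having the event on drug. This needs no assumed event rate.

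**Does a split lose rows?** If both columns use the same 36 patients as denominator and the 10% rule stays on the total, the total is never smaller than the pre-procedure count. Any event with 4 or more patients before the procedure therefore also has 4 or more in total, and no row drops out.

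**Is the split given elsewhere?** SAP 9.2.4.2 gives a relatedness view for serious events and an open-ended category of other events. It names nothing specific for common non-serious ones. No visible section defines treatment-emergent events or separates an on-drug from a post-operative period.

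**The case against.** The strongest reply is that this is read from a title. No table shell is shown, and a title that is silent on columns does not exclude period or relatedness columns. The protocol available is a synopsis with a schedule, and the SAP cites protocol text that is not in it, so adverse event definitions may exist elsewhere. That stands, and it is why the point is limited to the table as titled.

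A second reply is that the sponsor chose a window running to 28 days after the last dose, and that post-operative tolerability is a fair question for a preoperative drug. That also stands. It supports keeping the all-period total, but is no reason to withhold the split. A split separates timing, not cause, and a late drug effect can still fall after surgery.

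Third, safety is descriptive: "No inferential statistics will be performed for baseline variables or safety variables, unless otherwise specified". No decision rule uses Table 4. This limits the weight of the point.

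A reader might infer from the calendar share that about half of the reported events would be surgical. The documents do not support that: days are not events, and four of the five post-baseline assessments fall on drug. A reader might also want a probability that a purely surgical event enters the table. With assumed post-operative rates of 5% to 20% and 18 to 36 patients operated, the binomial probability of at least 4 patients runs from 0.01 to 0.95. A range that wide shows only that the documents do not settle the size.

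**Conclusion.** The point holds as a minor, inexpensive improvement of optional weight. As titled, Table 4 can put common non-serious surgical events and on-drug events of operated patients in one row, under an objective framed as tolerability to the drug and without a comparator.

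The conclusion rests on two assumptions: that the unseen table has no period columns, and that a material number of patients are operated on at the end of treatment. The documents confirm neither.

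It would go too far to say that Table 4 will misrepresent tolerability, or that the SAP ignores attribution. Serious related events, discontinuations and deaths are reported separately in 9.2.4.2, and the biomarker analyses do not depend on this table.

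**What to change.** Keep the all-period total in Table 4, with the 10% rule applied to it, and add two columns by date of onset:

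1. First dose to start of surgery or biopsy, or to 28 days after the last dose if neither is done.
2. Start of surgery or biopsy to 28 days after the last dose, labelled as events of drug and/or surgical origin, so that late drug effects are not dismissed.

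Use the same denominator throughout and count each patient once in the total. Show the numbers operated and biopsied in the header, and relatedness where it was recorded. If onset dates were not recorded, assign each event by the visit at which it was first reported: D7 to D28 for column 1, follow-up for column 2.

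The cost is a sentence or two of SAP text and two columns, with no new samples, visits or patients. The date of the procedure is already needed for the deviation check in SAP 8. The downside is a wider table with small counts per cell.

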9.2.2 Patient baseline characteristics

9.2.3 Biomarker analysis

9.2.3.1 *Primary analysis*

9.2.3.2 *Secondary analyses*

9.2.3.3 *Subset and covariate analysis*

9.2.3.4 *Pharmacokinetic/pharmacodynamic analysis*

9.2.3.5 *Pharmacokinetic-pharmacodynamic modeling (PBMC modeling)*

9.2.4 Safety analysis

9.2.4.1 *Treatment exposure analysis*

(Treatment delays, reductions and discontinuations, duration in days and strength of the dose received).

9.2.4.2 *Analysis of adverse effects*

(All serious related adverse effects, discontinuations, deaths and other relevant events).

9.2.4.3 *Analysis of concomitant medication received*

9.2.4.4 *Analysis of the physical examination and other safety-related remarks*

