4.2.3 Safety variables

- To test the tolerability for all AZD2281-treated patients measured as per Common Terminology Criteria for Adverse Events (CTCAE v.4).

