7.2 Populations for analysis

(ICH E3; 9.7.1, 11.4.2.5. ICH E9; 5.2)

Full analysis set

This set will include all the patients who have received the treatment. This set will also be the safety analysis set.

Per protocol set

This set will include all the patients of the full analysis set that do not have major protocol violations that may affect the assessment of treatment in the primary variable (e.g., non-evaluable patients for

biomarkers). The definition of these deviations is described in section 9.1. For the analysis of secondary variables, the number of evaluable patients for a certain biomarker analysis set will be considered.

Sensitivity analysis

The primary biomarker analysis (significant inhibition of cyclin D1, Ki67 and active caspase-3) and the secondary analyses will be performed in the full analysis set and the per protocol population.

The safety analyses will be performed in the full analysis set.

PKD population

We propose to analyze and model pharmacokinetics (PK), pharmacokinetics-pharmacodynamic (PBMC) and AZD2281 concentration, considering all patients with a complete treatment concentration-time profile.

Analyses will not be repeated between different analysis populations if they only differ by 10% patients. The largest analysis population will be used for the analyses.

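### The SAP guarantees reporting of serious adverse events only when they are related, its one adverse-event table starts at 4 of 36 patients, and no listed output uses CTCAE grade

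*SAP*

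**What the plan says.** Tolerability up to 28 days after the last dose is a secondary objective (SAP 4.1). SAP 4.2.3 measures it by CTCAE v.4 in all treated patients, and SAP 7.2 defines the safety set the same way: "This set will include all the patients who have received the treatment. This set will also be the safety analysis set".

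The reporting sits in two layers of SAP section 9:

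- **9.1, Summary of analysis.** This is introduced by "This analysis will show the following tables and figures", and the only adverse-event item in the list is "Table 4. Adverse events observed in the study, occurred at least in 10% of patients. Descriptive statistics. Safety analysis". It sets no limit by seriousness or causality.
- **9.2.4.2, Analysis of adverse effects.** This belongs to the part headed "9.2 Study full analysis". Its whole content is "All serious related adverse effects, discontinuations, deaths and other relevant events". It states no frequency cut-off and does not define which other events count as relevant.

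Neighbouring subsections cover treatment exposure (9.2.4.1, including delays, reductions and discontinuations), concomitant medication (9.2.4.3), and physical examination with other safety remarks (9.2.4.4). None of them commits to all adverse events, to all serious events whatever the cause, or to a breakdown by grade.

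**The concern.** Both filters act on the events that a small pre-operative study is most likely to see only once or twice.

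The notes to the study procedure table (SAP 5.1) place the surgical or biopsy sample within 24 hours of the last dose. For patients who have surgery, the post-operative period then lies inside the 28-day safety window. Events in that period can plausibly be put down to the operation, and such an attribution takes a serious event out of the only category of serious events that 9.2.4.2 names. The study is an "open-label, non-randomized, uncontrolled, multicenter phase 0 study that will enroll approximately 36 patients", so relatedness is judged unblinded and without a comparator.

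At stake is the completeness of the tolerability result. If the stated rules are followed literally, an observed serious or grade 3 or higher event may not be reported, or its inclusion may be decided under the catch-all after the data are known. CTCAE is a grading scale, so a CTCAE endpoint with no output by grade is not fully delivered.

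**Working it through.** The plan gives no calculated figure to reproduce here. The only number is the 10% threshold.

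**Inputs.** Planned patients: 36 (SAP 5.1). Denominator: all treated patients (SAP 7.2). Table 4 threshold: at least 10% of patients (SAP 9.1). True event rates: not in the documents; assumed, and shown as a range.

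**Step 1: the threshold as a count.** 0.10 × 36 = 3.6, so the smallest qualifying count is 4 (4/36 = 11.1%). Counts of 1, 2 and 3 (2.8%, 5.6%, 8.3%) are left out. Enrolment is approximate, but the count stays at 4 for any denominator from 31 to 40; at exactly 30 it is 3.

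**Step 2: one event taken through the rules.** Consider a serious, non-fatal event in 1 to 3 patients, attributed to surgery, with onset after the last dose and before day 28 of follow-up.

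| Reporting rule | Is the event guaranteed a place? |
|---|---|
| Table 4 (9.1) | No, fewer than 4 patients |
| Serious and related (9.2.4.2) | No, judged unrelated |
| Discontinuations (9.2.4.1, 9.2.4.2) | No, dosing has ended |
| Deaths (9.2.4.2) | No, non-fatal |
| Other relevant events (9.2.4.2) | Undefined |
| Other safety remarks (9.2.4.4) | Undefined |

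A non-serious grade 3 event in 1 to 3 patients after dosing fares no better, even if it is judged related, because 9.2.4.2 names relatedness only together with seriousness and nothing is listed by grade.

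**Step 3: how often an observed event falls below the Table 4 cut-off.** With X ~ Binomial(36, p):

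- P(seen at all) = P(X ≥ 1) = 1 − (1 − p)^36
- P(in Table 4) = P(X ≥ 4) = 1 − Σ C(36,k) p^k (1 − p)^(36−k), k = 0 to 3
- P(seen, not in Table 4) = P(X ≥ 1) − P(X ≥ 4)

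| Assumed true rate | Seen at all | In Table 4 | Seen, not in Table 4 |
|---|---|---|---|
| 3% | 66.6% | 2.2% | 64.4% |
| 5% | 84.2% | 10.4% | 73.9% |
| 8% | 95.0% | 32.5% | 62.6% |
| 10% | 97.7% | 49.1% | 48.6% |
| 15% | 99.7% | 80.9% | 18.8% |
| 20% | 99.97% | 94.8% | 5.2% |

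For p = 5%: 1 − 0.95^36 = 0.842; P(X ≥ 4) = 0.104; difference before rounding 0.739.

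**Step 4: what a count of 3 can mean.** The exact 95% interval for 3 of 36 is 1.8% to 22.5%. An event left out of Table 4 is therefore compatible with a true rate well above 10%.

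**Step 5: effect of removing the cut-off.** A table with no threshold shows every event seen at least once. The chance of appearing rises from 10.4% to 84.2% at a true rate of 5%, and from 49.1% to 97.7% at 10%.

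**The case against.** The strongest reply is that this is loose wording rather than exclusion. Several parts of it stand:

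- The 10% limit belongs to a summary table. The full analysis in 9.2.4.2 states no frequency threshold.
- Table 4 covers events of any seriousness or cause, so an unrelated serious event in 4 or more patients would appear there.
- Deaths and discontinuations are reported regardless of cause.
- The catch-all could admit a serious surgical complication on an ordinary reading.
- Tolerability is a secondary objective and safety analysis is descriptive unless otherwise specified (SAP 7.1). Without a control arm, no table could show whether the drug adds to complications.
- The event rates are assumed. They measure the Table 4 cut-off only, not the effect of the relatedness filter.
- The supplied protocol is a synopsis and a schedule, and SAP 7.5 refers to protocol text not supplied. The gap can be asserted only for the documents at hand.

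A reader might infer that serious events are reported only if related, that uncommon and surgical events are removed from the tolerability result, or that surgically attributed events are the typical case. The documents do not support these readings. Nothing excludes such events, and no rate of surgical complications is given. Sampling may also be by biopsy rather than surgery, and the deviation table (SAP section 8) works with a margin of 4 days after the end of treatment.

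What the reply does not remove is that relatedness and the 10% cut-off are written rules. An undefined catch-all guarantees nothing and leaves inclusion open until the data are known.

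**Conclusion.** The concern holds as a gap in commitment. A non-fatal serious or high-grade event in 1 to 3 of 36 patients, attributed to surgery and arising after dosing but within 28 days of the last dose, has no guaranteed place in the report. The endpoint defined by CTCAE has no listed output by grade.

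The size rests on 36 treated patients and on assumed true rates: 74% of trials at 5%, 63% at 8% and 49% at 10% would observe an event that stays below the Table 4 cut-off. The relatedness filter cannot be quantified from the documents.

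That the tolerability conclusion will be too favourable does not follow. It would require the catch-all to be applied narrowly or Table 4 to carry the result alone. The primary biomarker analysis is not affected. The change should be made, because it closes the gap with data already scheduled for collection.

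**What to change.** - In SAP 9.2.4.2, replace the item on related serious effects with all serious adverse events and all CTCAE grade 3 or higher events regardless of attribution. Show relatedness and timing relative to surgery for each.
- Define the catch-all, or limit it to events not covered by the other items.
- In the full analysis (9.2), add a table of all adverse events by term and worst CTCAE grade with no frequency cut-off.
- Keep Table 4, with its 10% limit, as the summary in 9.1.

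The cost is SAP wording and a longer table that includes events unrelated to the drug. No new data are needed: safety is already assessed by CTCAE during treatment and at the visit 28 days after the last dose.
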